APPENDIX G: PATIENTS

SAMPLE TRANSFUSION PLAN: LTB AND HTB 77

8 of 77 Version 3.0; 31 July 2023

VV-CLIN-180184 3.0

LIST OF TABLES

Table 1 1.	Schodula of Events Drimony and Evetancian Treatment Davids 10
Table 1-1:	Schedule of Events, Primary and Extension Treatment Periods 19
Table 1-2	Schedule of Events – Optional Prolonged Treatment Period
Table 6-1	Acceptable contraceptive methods
Table 7-1	Suggested Dose Modifications for Treatment Related AEs43
	LIST OF FIGURES
Figure 1:	PKR Activation as a Strategy to Reduce the Anemia Associated with Myelodysplastic Syndrome
Figure 2:	Healthy Volunteers PK/PD Simulations Identifies Potential Phase 2 Dose Selections
Figure 3:	Schema31

LIST OF ABBREVIATIONS AND DEFINITION OF TERMS

2,3-DPG 2,3-diphosphoglycerate

AE adverse event

ALT alanine aminotransferase AML acute myeloid leukemia

ATC Anatomical Therapeutic Chemical

ATP adenosine triphosphate

AUC area under the plasma concentration-time curve

BMA bone marrow aspirate
BMB bone marrow biopsy
BMI body mass index

CFR Code of Federal Regulations COVID-19 coronavirus disease 2019 CRA clinical research associate

CTCAE Common Terminology Criteria for Adverse Events

CYP cytochrome P450
DLT dose-limiting toxicities
ECG Electrocardiogram

eCRF electronic case report form

EOT end of treatment

ESA erythropoiesis-stimulating agents FDA Food and Drug Administration

FIH First-in-Human

GCP Good Clinical Practice
HepBsAg hepatitis B surface antigen
HepBcAb hepatitis B core antibody

Hb Hemoglobin HCV hepatitis C virus

HI-E Hematologic improvement-erythroid HIV human immunodeficiency virus

HTB High transfusion burden ICF informed consent form

ICH International Council for Harmonisation

IEC Independent Ethics Committee

IPSS-R International Prognostic Scoring System-Revised

IRB Institutional Review Board

IUD intrauterine device

IWG International Working Group

LDH lactate dehydrogenase
MAD multiple ascending dose
LTB low transfusion burden

MedDRA Medical Dictionary for Regulatory Activities

MDS myelodysplastic syndromes NCI National Cancer Institute NTD non-transfusion dependent

O₂ Oxygen

P₅₀ partial pressure of O₂ at which Hb O₂ saturation of 50% is achieved

PD pharmacodynamic(s) PK pharmacokinetic(s)

PKR pyruvate kinase-red blood cell

PROMIS Patient-Reported Outcomes Measurement Information System

PT preferred term
QD once daily
QoL Quality of Life

QTcF QT interval corrected using Fridericia's correction formula

QUALMS The Quality of Life in Myelodysplasia Scale

RBC red blood cells

RBC-TI RBC transfusion independence

ROS reactive oxygen species
SAD single ascending dose
SAE serious adverse event
SAP statistical analysis plan
SCD sickle cell disease
SOC system organ class

SOP standard operating procedure SRC Safety Review Committee TD transfusion dependent

TEAE treatment-emergent adverse event

TESAE treatment-emergent serious adverse events

TIBC Total Iron Binding Capacity t-MDS therapy-associated MDS ULN upper limit of normal WBC white blood cell

WHO World Health Organization

WHODrug World Health Organization Drug Dictionary

1.0 PROTOCOL SUMMARY

1.1 Synopsis

Title: A Phase 2 Open-Label Study to Evaluate Etavopivat for the Treatment of Anemia in Patients with Myelodysplastic Syndromes (MDS)

Rationale:

Etavopivat (FT-4202) is a potent, selective, orally bioavailable, small-molecule activator of pyruvate kinase -red blood cell (PKR) being developed by Forma Therapeutics, Inc and is intended for use as a treatment for the anemia of MDS, inherited hemolytic anemias, and other refractory anemias.

Objectives and Endpoints:

Objectives	Endpoints									
Primary	,									
To assess hematologic improvement based on an erythroid response (HI-E) for ≥ 8 weeks duration in patients with MDS within 24 weeks of etavopivat treatment	The HI-E for ≥ 8 weeks within 24 weeks of etavopivat. This endpoint will be based on the combined incidence of: Non-transfusion dependent (NTD) patients: ≥ 1.5 g/dL increase in hemoglobin (Hb) from baseline maintained ≥ 8 consecutive weeks and no transfusion of RBC units for anemia over a continuous 8-week treatment period Low transfusion burden (LTB) patients: absence of any transfusion for ≥ 8 consecutive weeks High transfusion burden (HTB) patients: reduction by ≥ 50% of red blood cell (RBC) units for ≥ 8 consecutive weeks									
Secondary										
• To assess HI-E for ≥ 8 weeks duration in this population of patients within 16 and 48 weeks of etavopivat treatment	 The HI-E for ≥ 8 weeks within 16 and 48 weeks of etavopivat This endpoint will be based on the combined incidence of: ○ NTD patients: ≥ 1.5 g/dL increase in Hb from baseline maintained ≥ 8 consecutive weeks and no transfusion of RBC units for anemia over a continuous 8-week treatment period ○ LTB patients: absence of any transfusion for ≥ 8 consecutive weeks ○ HTB patients: reduction by ≥ 50% of RBC units for ≥ 8 consecutive weeks 									
To assess HI-E for ≥ 16 weeks duration in this population of patients within 24 and 48 weeks of etavopivat treatment	 The HI-E for ≥ 16 weeks within 24 and 48 weeks of etavopivat This endpoint will be based on the combined incidence of: ○ NTD patients: ≥ 1.5 g/dL increase in Hb from baseline maintained ≥ 16 consecutive weeks and no transfusion of RBC units for anemia over a continuous 8-week treatment period ○ LTB patients: absence of any transfusion for ≥ 16 consecutive weeks ○ HTB patients: reduction by ≥ 50% of RBC units for ≥ 16 consecutive weeks 									

Secondary, continued	
• To assess the safety and tolerability of etavopivat in patients with MDS	 Incidence of adverse events (AEs), serious adverse events (SAEs), and AEs related to etavopivat Number of premature discontinuations, dose interruptions, and dose reductions
To assess additional measures demonstrating potential clinical benefit	 Overall response rate (2006 International Working Group [IWG] Criteria) (see Appendix A) Duration of response (2006 IWG Criteria) Reduction in RBC transfusions and rate of RBC transfusion independence ≥ 8 weeks in patients with LTB or HTB at study entry. Increase in neutrophils and/or platelets counts Decrease in ferritin and transferrin saturation (TSAT) Decrease in iron chelation therapy Overall survival
Pharmacokinetic / Pharmacodynamic	
To assess the pharmacokinetic (PK) and pharmacodynamic (PD) properties of etavopivat in patients with MDS	 Etavopivat plasma PK parameters (including but not limited to): maximum observed plasma concentration, time to maximum observed plasma concentration, area under the plasma concentration-time curve from time zero until the last quantifiable time point (AUC_{0-last}), from time zero to infinity (AUC_{0-inf}), for a dosing interval (AUC_{tau}/AUC₀₋₂₄). RBC 2,3-diphosphoglycerate (2,3-DPG) and adenosine triphosphate (ATP) levels over time
Exploratory	
To examine safety trends in patients with MDS receiving etavopivat	Assessment of vital signs, clinical laboratory findings, and physical examination findings
To assess changes in quality-of-life in patients with MDS taking etavopivat	 Change from baseline in Patient-Reported Outcome Measurement Information System (PROMIS) Fatigue Scale at Weeks 16, 24, and 48 Change from baseline in The Quality of Life in Myelodysplasia Scale (QUALMS) patient-reported outcome assessment at Weeks 16, 24, and 48
To characterize the biological effects of etavopivat treatment in patients with MDS	 Cell colony analysis of bone marrow progenitors Cytomorphology (blast, M/E, and ringed sideroblast determination) and cytogenetics of bone marrow Markers of ineffective erythropoiesis and iron metabolism Cancer-associated mutations and/or genetic alterations in responding and non-responding patients Flow cytometry analysis of terminal erythroid differentiation (EU Only)

Overall Design:

This study is a multicenter, open-label, Phase 2 study in adult patients with very low, low risk, or intermediate risk MDS per the International Prognostic Scoring System-Revised (IPSS-R) classification (see Appendix B).

The study will enroll up to 45 patients with MDS who will be evaluated for HI-E response composite derived from the MDS IWG 2018 criteria (modified by Platzbecker et al. 2019)

(see Appendix A). HI-E response assessment will be based on the individual patient's transfusion history in the 16 weeks prior to enrollment:

- NTD patients (received ≤ 2 RBC units for anemia within the prior 16 weeks): Hb increase of ≥ 1.5 g/dL over a continuous 8-week treatment period and no transfusion of RBC units for anemia over a continuous 8-week treatment period
 - Approximately 15 patients meeting the criteria for NTD may be enrolled in this study
- LTB patients (received 3 to 7 RBC units within the prior 16 weeks): No transfusion of RBC units for anemia over a continuous 8-week treatment period
 - Approximately 15 patients meeting the criteria for LTB may be enrolled in this study
- HTB patients (received ≥ 8 RBC units in the prior 16 weeks): ≥ 50% reduction in RBC units transfused over a continuous 8-week period.
 - Approximately 15 patients meeting the criteria for HTB may be enrolled in this study

Patients will be enrolled into a 48-week treatment period, including a 24-week Primary Treatment period and a 24-week Extension Treatment period. Patients demonstrating clinical benefit at the end of the 48-week treatment period may continue treatment. The dose of etavopivat is 400 mg once daily (QD) administered continuously; the selection of the starting dose is based on results from a Phase 1 study in patients with sickle cell disease (SCD) who were not receiving chronic RBC transfusions.

After the 6th patient completes a minimum of 4-weeks of daily etavopivat treatment, a safety review meeting will be held to confirm that the safety, exposure, and pharmacological response (PK/PD profile) are consistent with prior experience of etavopivat dosing in healthy volunteers and patients with sickle cell disease or thalassemia.

A futility assessment will be triggered when 15 patients across all strata or 8 patients in a single stratum reach 24 weeks of treatment, whichever occurs first. If both criteria are met at the same time, the overall futility assessment will be performed.

The futility criterion is defined as follows:

- All strata (n=15): ≤ 3 responses meeting HI-E criteria, sustained from Week 16 to Week 24.
- Single stratum (n=8): 0 (zero) responses.

If either the overall, or single stratum, futility criterion is met, enrollment may discontinue due to futility. Further enrollment may be considered if it is restricted to specific subsets of patients based on prior transfusion history. If neither criterion is met, enrollment will continue until a total of 45 response-evaluable patients are available at Week 24.

Enrollment will not pause during assessment periods unless futility analysis suggests clinical need to pause.

At final analysis, the study will evaluate the rate of MDS IWG 2018 criteria responses in the pooled, open-label etavopivat-treated patients versus a null-assumed rate of 20%.

Treatment Duration: Duration of study treatment will be up to 48 weeks, including 24 weeks in the Primary Treatment period and 24 weeks in the Extension Treatment period. Patients who demonstrate clinical benefit at 48 weeks of treatment, based on their MDS response assessment, may continue treatment until the patient experiences unacceptable

toxicities, disease progression, withdraws consent, or meets any other discontinuation criteria (Section 7.2.1).

Study Duration: Duration of study for an individual patient is approximately 58 weeks and includes a Screening Period (up to 6 weeks before study treatment), the 24-week Primary Treatment period, the 24-week Extension Treatment period, and Safety Follow-up visit occurring 28 days (+ 7 days) after last dose of study drug. The study duration will be greater than 58 weeks in patients who continue study treatment beyond the planned 48-week treatment period due to clinical benefit.

Number of Participants

Approximately 45 patients will be enrolled.

Key Inclusion Criteria

Type of Participant and Disease Characteristics

- 1. Documented diagnosis of idiopathic/de novo MDS according to World Health Organization (WHO) classification (see Appendix C) that meets the IPSS-R classification (see Appendix B) of very low, low, or intermediate risk disease, and:
 - < 5% blasts and no Auer rods in bone marrow based on local pathology review
 - < Intermediate risk cytogenetic abnormalities per IPSS-R (see Appendix B)
- 2. Anemia defined as:
 - NTD: Subjects with mean Hb concentration < 10.0 g/dL of 2 measurements (1 performed within 3 days prior to W1D1 and the other performed 7 to 28 days prior to W1D1, not influenced by RBC transfusion within 7 days of measurement) and < 3 RBC transfusions for anemia in the prior 16 weeks before W1D1 of etavopivat dosing

OR

- Transfusion Dependent: Subjects having received ≥ 3 units of RBCs for the treatment of anemia within 16 weeks prior to W1D1
- 3. Serum erythropoietin level > 200 U/L, OR, if ≤ 200 U/L, subject is non-responsive, refractory, or intolerant to erythropoiesis-stimulating agents, or erythropoiesis-stimulating agents are contraindicated or unavailable.
- 4. Eastern Cooperative Oncology Group performance status of ≤ 2 (see Appendix D)
- 5. Subject is non-responsive, refractory, or intolerant to luspatercept, or luspatercept is contraindicated or not indicated.
- 6. No alternative treatment options are available and/or appropriate for the subject, at the discretion of the investigator.
- 7. Patient is willing and able to adhere to the study visit schedule and other protocol requirements

Key Exclusion Criteria

MDS History

1. MDS associated with del 5q cytogenetic abnormality and known TP53 abnormality

- 2. Therapy-associated MDS (eg. t-MDS) that is known to have arisen as the result of chemical injury or treatment with chemotherapy and/or radiation for other diseases
- 3. Known history of acute myeloid leukemia (AML)
- 4. Any diagnosis of myelodysplastic/myeloproliferative neoplasms

Medical Conditions

- 5. Known clinically significant anemia due to iron, vitamin B12, or folate deficiencies, or autoimmune or hereditary hemolytic anemia, or gastrointestinal bleeding
- 6. Absolute neutrophil count $< 500/\mu L (0.5 \times 10^9/L)$
- 7. Platelet count $< 50,000/\mu L (50 \times 10^9/L)$ without transfusion within 14 days
- 8. Hepatic dysfunction characterized by any one of the following:
 - Alanine aminotransferase (ALT) $> 3.0 \times$ upper limit of normal (ULN)
 - Total bilirubin $> 2.0 \times ULN$ (in the absence of cholestasis)
 - History and/or evidence of cirrhosis

Novo Nordisk Safety Committee

Novo Nordisk will perform ongoing safety surveillance. Safety surveillance activities encompass the regular periodic safety data review from clinical trials, literature surveillance and safety information derived from other sources.

If new safety signals are identified, these will be evaluated by the etavopivat internal safety committee.

The safety committee is cross-functional and the only Novo Nordisk body responsible for providing integrated assessments of safety data and endorsing appropriate actions in case of a safety signal.

Subsequently, safety information is communicated and reported to health authorities, ethics committees and investigators, as relevant and in accordance with regulatory requirements.

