Coagulation parameters ^g	X			X						X			X												X	X	
Serum Pregnancy Test ^j	X																										
Serum Erythropoietin	X																										
Serum Virology ^g	X																										

Forma Therapeutics, Inc. Clinical Study Protocol 4202-ONC-203

Assessments	Screen		Primary treatment period												Extension treatment period											Safety follow- up visit
Study Day/Week(s):	D-42	W1D1	W2 D1	W4 D1	W6 D1	W8 D1	W10 D1	W12 D1	W14 D1	W16 D1	W20 D1	W22 D1	W24 D1	W26 D1	W28 D1	W30 D1	W32 D1	W34 D1	W36 D1	W38 D1	W40 D1	W42 D1	W44 D1	W46 D1	W48 D1	W52 D1
	to -1		(±3 D)	(±3 D)	(±3 D)	(±3 D)	(±3 D)	(±3 D)	(±3 D)	(±3 D)	(±3 D)	(±3 D)	(±3 D)	(±3 D)	(±3 D)	(±3 D)	(±3 D)	(±3 D)	(±3 D)	(±3 D)	(±3 D)	(±3 D)	(±3 D)	(±3 D)	(±3 D)	(±3 D)
Transfusion Data Collection and Assessment		Assess and record on ongoing basis until end of treatment visit or 8 weeks after last dose of etavopivat, whichever comes first. Clinical staff should confirm if any transfusions were received by the patient (including any at outside local institutions in between study visits).																								
PROMIS Fatigue Scale	X	X		X		X		X		X	X		X				X				X				X	X
The QUALMS	X	X		X		X		X		X	X		X				X				X				X	X
MDS Baseline Assessment (IPSS-R) ^k	X																									
MDS Response Assessment ¹										X			X m												X	X
Exploratory Studies n	X	X		X						X	X		X				X				X				X	
PD Sampling °		X	X	X																					X	X
PK Sampling ^p		X	X	X									X												X	
Study Drug Administration		X										Dai	ly throu	ghout ti	reatmen	t period										
Survival q												Q 3	months	after E	nd of Ti	rial visit					•				•	

Abbreviations: BMI = body mass index; D = day; ECOG PS = Eastern Cooperative Oncology Group performance status; ECG = electrocardiogram; ESA = Erythropoiesis-stimulating agent; Hb = hemoglobin; ICF = informed consent form; IPSS-R = International Prognostic Scoring System-Revised; MDS = myelodysplastic syndromes; PK/PD = pharmacokinetics/pharmacodynamics; PROMIS = Patient-Reported Outcomes Measurement Information System; RBC = red blood cell; The QUALMS = The Quality of Life in Myelodysplasia Scale; W = week.

Note: Study visits after W1D1 must be conducted within ± 3 days of the scheduled visit. For the purposes of assessments and analyses in this study, 4 weeks = 1 month.

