8.2.2 Assessment of Transfusions

RBC, and platelet, transfusions will be recorded on an ongoing basis throughout the study as indicated in Table 1-1 and Table 1-2. For any RBC, and platelet, transfusions received during the study, collect Hb and platelet values prior to transfusion, the number of units transfused, and the dates of transfusion. If available, the Hb/hematocrit of the transfused unit should also be collected.

8.2.2.1 LTB/HTB Patient Transfusion Treatment Plan:

Each patient will have an individualized transfusion treatment plan in place prior to study treatment (see Appendix G). This treatment plan assumes a pre-transfusion Hb value is collected within 7 days of a scheduled transfusion. The decision on the RBC transfusion schedule and amount of RBC units to transfuse will be based on the following parameters:

- 1) A baseline pre-transfusion Hb threshold determined by the mean of all documented pretransfusion Hb values during the 16 weeks prior to start of study treatment.
- 2) During treatment, if the pre-transfusion Hb level is increased by ≥ 1 g/dL compared to the pre-transfusion Hb threshold for that patient, transfusion may be delayed by a minimum of 7 days and/or the number of units transfused may be reduced by 1 or more RBC units.

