3.3. Baseline Definitions

Baseline values for Hb will be defined as the mean of the screening and Day 1 pre-treatment values. If one of the two assessments is missing, then a single assessment prior to the start of study treatment will be defined as baseline.

History of RBC transfusions will be gathered for each patient for up to 16 weeks before start of study treatment. Baseline RBC transfusion burden units per 8 weeks will be defined as the summed units transfused in the 8 weeks up to pre-dose Day 1 (Rel Day -55 to 1).

For all other analyses, baseline will be defined as the most recent non-missing measurement prior to the first administration of study drug.

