4.2.1. Analysis of Primary Endpoints

4.2.1.1. HI-E Response and MDS assessments

The proportion of patients with HI-E response ≥ 8 weeks within 24 weeks of etavopivat treatment will be analyzed across the pooled strata and within each stratum. Patients will be considered responders if they satisfy HI-E criteria during any continuous ≥ 8 -week treatment interval up to W24D1.

HI-E criteria are defined based on the patient's transfusion history stratum at D1:

NTD: A patient is considered a responder where at least one continuous interval ≥ 8 weeks occurs where all of the following criteria are met:

- Hb is increased by ≥ 1.5 g/dL relative to baseline at 2 or more consecutive visits
- Relapse date (date of first Hb measurement with < 1.5 g/dL change from baseline following the qualifying increase) occurs at least 8-weeks after the first incidence of qualifying Hb increase
- Patient is free of RBC transfusions

LTB: A patient is considered a responder if they are free of RBC transfusions over any continuous 8-week period.

HTB: A patient is considered a responder if they have a $\geq 50\%$ reduction in RBC transfusion burden relative to baseline RBC transfusion burden per 8 weeks over any continuous 8-week period.

Percent reduction in RBC transfusion burden is calculated for all rolling 56-day intervals in the 24-week primary treatment period (i.e. Days 2-57, Days 3-58,..., Days 113-168) as

$$-100 \times \frac{RBC \text{ units transfused in 56 day interval} - \text{Baseline RBC transfusion burden per 8 weeks}}{\text{Baseline RBC transfusion burden per 8 weeks}}$$

The numerator for the response rate will be the total number of responders (summed across all baseline transfusion categories). The denominator will be the number of patients in the EES.

MDS baseline assessment including the score based on Revised International Prognostic Scoring System (IPSS-R) for MDS and MDS response assessment will be presented in data listings.

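### The HTB response rule can score an unchanged 4-weekly transfusion schedule as a 50% reduction when one transfusion is a single day late

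*Protocol*

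**What the plan says.** Protocol 1.1 and 4.1 place a patient in the HTB stratum at 8 or more RBC units in the prior 16 weeks. The response is a "≥ 50% reduction in RBC units transfused over a continuous 8-week period".

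The SAP makes this exact to the day.

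- **Baseline (SAP 3.3):** one fixed window, "the summed units transfused in the 8 weeks up to pre-dose Day 1 (Rel Day -55 to 1"). There is no Day 0, so this is 56 days.
- **Response (SAP 4.2.1.1):** a reduction of at least 50% "relative to baseline RBC transfusion burden per 8 weeks over any continuous 8-week period".
- **Windows (SAP 4.2.1.1):** "Percent reduction in RBC transfusion burden is calculated for all rolling 56-day intervals in the 24-week primary treatment period", running from Days 2-57 to Days 113-168.

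One qualifying window is enough. The rule has no date tolerance, no confirmation and no second window.

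Appendix A, which the protocol cites for the response criteria, sets a longer period. For HTB it accepts a 50% reduction (its minor response) only over at least 16 weeks, compared with the 16 weeks before treatment. Its 8-week criterion for HTB is complete absence of transfusions (its major response).

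**The concern.** Two units every 28 days gives exactly 8 units in 16 weeks, so such a patient is HTB by the smallest margin. Two 28-day intervals make exactly 56 days, the length of the scoring window, and each window holds two transfusions. Losing one of the two is a 50% reduction. The rule therefore has no slack for this pattern: a calendar shift of one day can turn a non-responder into a responder while the dose of blood and the interval are essentially the same.

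The HTB response feeds the pooled primary rate, which protocol 9.6.1 tests against 20%, and the futility count in SAP 3.11. For 4-weekly patients it would partly measure movement of dates rather than drug effect, and always in the favourable direction, because the lowest of many windows is compared with one fixed baseline.

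**Working it through.** **The plan's own figure.** Protocol 9.3 states 87.3% power for N = 45, 20% against 40%, one-sided 0.025, exact binomial. The exact rule is at least 15 responders of 45: P(X ≥ 15 | 0.20) = 0.02499 and P(X ≥ 15 | 0.40) = 85.7%. The one-sample normal approximation gives about 87.25%, which matches the stated value. I use the exact rule of 15 of 45 below.

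**One worked patient.** Baseline is 2 transfusions × 2 units = 4 units. Transfusions fall on Days 1, 29 and 58 (the last was due on Day 57). The window Days 2-57 contains only Day 29, so 2 units. By the SAP formula, −100 × (2 − 4)/4 = 50%: a responder. With exact dates every window holds 4 units and the reduction is 0%.

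**All positions of a single one-day delay.** Let the late transfusion be due on Day x, for x = 2 to 168 (167 cases, covering all 28 start phases).

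- *Schedule resumes.* The second predecessor is on Day x − 56 and the late one on Day x + 1. The 56 days between, x − 55 to x, hold one transfusion. They fit inside Days 2-168 when 57 ≤ x ≤ 168: 112 cases, or 67%.
- *Delay carries forward.* A second qualifying window, x − 27 to x + 28, fits when 29 ≤ x ≤ 140. The union is 29 ≤ x ≤ 168: 140 cases, or 84%.
- *No delay:* 0 of 167.

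Direct enumeration of all windows gives the same counts. Three or four units every 28 days behave the same way.

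**Why other schedules are spared.** A 3-weekly patient has two or three transfusions in the baseline window and qualifies only with one or none in 56 days. That needs two successive gaps totalling 57 days instead of 42, which is 15 days of slack. A 2-weekly patient has four at baseline and must fall to two, so three gaps must total 57 days instead of 42, again 15 days. Enumeration with a one-day delay gives 0 of 167 for both. In simulation with shifts up to ±3 days, the highest rate for either was 0.08%.

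**Repeated small shifts (assumed; the documents give no distribution).** The table shows the share of unchanged 4-weekly patients scored as responders.

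| Date movement | Around a fixed calendar | Carried forward |
|---|---|---|
| 10% of transfusions move up to ±1 day | 24% | 15% |
| 20% of transfusions move up to ±1 day | 44% | 28% |
| Every transfusion moves, ±1 to ±3 days | 86-93% | 71-81% |

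**Illustration for the planned test.** Assume 15 of 45 patients are HTB, a share s of them is 4-weekly, 90% of those are false responders, and everyone else responds at 20%. The pooled rate is 0.20 + (15/45) × s × (0.90 − 0.20).

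| s | Pooled rate | P(X ≥ 15 of 45) |
|---|---|---|
| 0 | 0.200 | 0.025 |
| 10% | 0.223 | 0.060 |
| 25% | 0.258 | 0.163 |
| 50% | 0.317 | 0.460 |

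The 90% is at the upper end of the previous table. With 24% instead, s = 25% gives 0.20 + (1/3)(0.25)(0.24 − 0.20) = 0.203, so the error would lie between 2.5% and 6.0%.

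**The same check over 16 weeks.** Baseline is 8 units in 112 days. A 50% reduction needs at most two transfusions in 112 days, so three successive gaps must total 113 days instead of 84: 29 days of slack. With a one-day delay at least 6 units remain, a 25% reduction at most. Delays of 1, 3 and 7 days give 0 responders in 167 cases.

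**The case against.** Several objections have force.

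- **Not every late transfusion counts.** A reader might infer that any one-day delay makes a responder. It does not: delays early in treatment leave no room for a full window inside Days 2-168, hence 67% and 84% rather than 100%.
- **The visit tolerance is not a transfusion tolerance.** The note to Table 1-1 says "Study visits after W1D1 must be conducted within ± 3 days of the scheduled visit". HTB scoring uses transfusion dates, and nothing ties these to study visits. The ±3 days therefore does not show how far transfusions move. Protocol 8.2.2.1 does say "transfusion may be delayed by a minimum of 7 days", but only after a rise in pre-transfusion Hb of at least 1 g/dL, which may be a drug effect. What stands is that no text fixes transfusion dates and that one day is enough.
- **The size is assumption.** The highest percentages need every transfusion to shift, and the share of 4-weekly patients is unknown. The figures show sensitivity and are not estimates.
- **The test may never be run.** SAP 1.1 was written after early termination for an abbreviated report. SAP 4.2.1.1 reports a proportion and states no test, although SAP 5.2 does not list the protocol test as dropped. A reader might infer that the trial's actual type I error is inflated by a known amount. The documents do not support that; the error figures describe the planned 45-patient test only. The upward bias in the reported HTB and pooled proportions remains.
- **The artefact would be visible.** SAP 4.2.2.1 tabulates units in fixed 8-week blocks and SAP 3.9 lists all data. That helps a careful reader but does not change who is counted as a responder.

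**Conclusion.** The defect is real and lies in SAP 4.2.1.1 read with SAP 3.3; the protocol sentence gives only the 8-week rule. For an unchanged 4-weekly HTB patient, one transfusion one day late produces a primary-endpoint response in 67% to 84% of positions, and nothing else in the documents blocks it. This part rests on arithmetic alone.

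The effect on the HTB and pooled rates is upward, but its size depends on the share of 4-weekly patients and the frequency of date shifts, neither of which is given. The range of 6% to 46% for the one-sided error holds only for the planned 45-patient test, with 10% to 50% of 15 HTB patients on a 4-weekly schedule and 90% of them false responders. It is not a statement about the terminated trial's result. The problem is also not independent of the mismatch with Appendix A: over that appendix's 16-week period it disappears for every delay tried.

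**What to change.** In SAP 4.2.1.1, reconcile the HTB rule with Appendix A. Score the reduction of at least 50% over a rolling window of at least 112 days within Days 2-168, against the units in the 16 weeks before treatment, and report the 56-day result next to it. If the 56-day rule stays primary, make the 16-week version a required sensitivity analysis and flag every HTB responder who qualifies only under the 56-day rule. Protocol 3.2 already contains a 16-week HTB response as a secondary endpoint, which SAP 5.2 drops.

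Lengthening only the treatment window, for example to 63 days against the 56-day baseline, is tempting but should be avoided. A weekly patient truly halved from 2 units to 1 would have 9 units against a cut of 8, and responds in 0 of 7 start phases instead of 7 of 7. One 8-day delay would still make 105 to 133 of 167 unchanged 4-weekly cases responders. The matched 16-week comparison keeps the true halvings tested.

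Cost: a few SAP sentences and a small programming change. Protocol 8.1.3 already collects at least 16 weeks of transfusion history. The date-imputation rule in SAP 3.9 is written for an 8-week baseline and needs a matching line. The downside is that shorter-lived HTB reductions no longer count, so the HTB rate may be lower. Because the protocol defines the endpoint over 8 weeks, the change should be recorded in SAP section 5.
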